3. LIST OF ABBREVIATIONS AND DEFINITIONS OF TERMS

The following abbreviations and specialist terms are used in this study protocol.

Abbreviation or Specialist Term Explanation arterial blood gas ABG ACE angiotensin converting-enzyme AE adverse event ALP alkaline phosphatase ALT alanine transaminase AST aspartate transaminase AT1R angiotensin II type 1 receptor BP blood pressure BUN blood urea nitrogen clinical research associate CRA CRF case report form DSMB data safety monitoring board ECG electrocardiogram ECMO extracorporeal membrane oxygenation eCRF electronic case report form EOS end of study FiO₂ fractional inspired oxygen GCP good clinical practice HR heart rate ICH International Conference on Harmonisation ICU intensive care unit IEC independent ethics committee INR international normalized ratio IRB institutional review board IV intravenous(ly) MAP mean arterial pressure mEq milliequivalent millimeter of mercury mmHg NE norepinephrine

Table 2:Abbreviations and Specialist Terms

NED	norepinephrine-equivalent dose
NIRS	near-infrared spectroscopy
PaCO ₂	carbon dioxide partial pressure
PaO ₂	arterial oxygen partial pressure
PE	physical exam
PELOD	Pediatric Logistic Organ Dysfunction
PIM2	Pediatric Index of Mortality 2
PRISM	Pediatric Risk of Mortality
РТ	prothrombin time
PTT	partial thromboplastin time
RAAS	renin angiotensin aldosterone system
RR	respiratory rate
SAE	serious adverse event
SGOT	serum glutamic-oxaloacetic transaminase
SOC	standard of care
SOP	standard operating procedures
VA	veno-arterial
VV	veno-venous
WBC	white blood cell

4. INTRODUCTION

4.1. Pediatric Shock Etiology

Shock, a life-threatening condition, is the clinical expression of circulatory failure that results in inadequate cellular oxygen utilization. In one subtype of shock, distributive shock, cardiac output is typically high and the main deficit lies in the periphery, with decreased systemic vascular resistance and altered oxygen extraction. Sepsis is a common cause of distributive shock.

The progression of shock in pediatric patients is unique from adults. Younger children are unable to significantly increase stroke volume in the face of a stress response, augmenting cardiac output instead by increased chronotropy. Early compensatory mechanisms like tachycardia are inadequate, and uncompensated shock ensues and downstream micro- and macroscopic perturbations occur. Cellular ischemia and the release of vasoactive metabolites and inflammatory mediators start to affect the microcirculation. If not reversed, multi-organ system failure can occur. The vascular endothelium of these patients is also immature and can display marked heterogeneity to the effects of circulating catecholamines or vasopressor support, leading to rapid and sometimes unpredictable changes from vasodilated to vasoconstricted or vice versa.

4.2. Treatment and Unmet Medical Need

Treatment of shock and sepsis in children involves a progression of interventions, beginning with establishing adequate ventilation and administering fluids and antibiotics. If patients do not respond to fluids, vasopressor or inotropic support may be used, including epinephrine (for cold shock) or norepinephrine (NE; for warm shock) infusions. Hydrocortisone may be administered if adrenal insufficiency is suspected. Vasopressor use has been reported in 21% of pediatric patients with shock (Fisher 2010).

The use of high dose catecholamines, such as epinephrine and NE, in patients with severe hypotension is associated with poor outcomes. The only other approved vasopressor that is not a catecholamine is vasopressin, which may reduce NE requirements in adult patients with severe hypotension (Bassi 2013, Neto 2012). However, high-dose vasopressin has been associated with myocardial ischemia and mesenteric ischemia (Russell 2011, Sharman 2008). Vasopressin is not indicated for pediatric use because the safety and effectiveness in patients with vasodilatory shock have not been established. One placebo-controlled study of arginine vasopressin in pediatric patients showed that while there was a statistically significant increase in mean arterial pressure (MAP) from baseline after 1 hour, there were no significant differences in the time to hemodynamic stability, organ failure-free days or ventilator-free days, length of intensive care unit (ICU) stay, and adverse events (AEs). The authors concluded that low-dose vasopressin did not demonstrate any benefits in pediatric vasodilatory shock (Choong 2009).

No product has been shown to effectively and safely treat pediatric patients with distributive shock who remain hypotensive despite treatment with fluids and catecholamines. Thus, there is a significant unmet need in this patient population. Pediatric sepsis is a significant healthcare burden. Based on the incidence of sepsis in children (Watson 2003), and the proportion of pediatric patients with severe sepsis who are reported to develop septic shock (Kutko 2003), the

annual incidence of septic shock in pediatric patients is estimated to be 2,065 to 12,390 in the US. While the outcomes for pediatric patients who remain hypotensive despite receiving fluid therapy and vasopressor therapy are not specifically described, the mortality rate for pediatric severe sepsis has ranged from 8.9% to 14.4% in recent years (Hartman 2013, Ruth 2014).

This study (LJ501-CRH02) will evaluate the safety and efficacy of LJPC-501 in pediatric patients 2 to 17 years old who remain hypotensive despite receiving fluid therapy and vasopressor therapy, and will be conducted in compliance with the protocol, good clinical practice (GCP), and all applicable regulatory requirements(s).

4.3. Angiotensin II Mechanism of Action

The active ingredient in LJPC-501 is the acetate salt of synthetic angiotensin II, an octapeptide identical to endogenous human angiotensin II. Angiotensin II is the major bioactive component of the renin-angiotensin-aldosterone system (RAAS System), and serves as one of the body's central regulators of blood pressure (BP). The RAAS system along with the arginine-vasopressin system and the sympathetic nervous system make up the three major counter-regulatory systems the human body utilizes to manage BP. Angiotensin II is a naturally occurring peptide hormone that regulates BP through activation of the angiotensin II type 1 receptor (AT1R). Through the AT1R, angiotensin II induces peripheral vasoconstriction, increases sodium and water retention, aldosterone release, and vasopressin release leading to increase in BP (Harrison-Bernard 2009, Basso 2001).

4.4. Nonclinical Experience with Angiotensin II

Extensive nonclinical studies are reported in the literature on angiotensin II that provide a comprehensive understanding of its pharmacodynamic, safety pharmacology, pharmacokinetic, and toxicology profile; these studies are described in the Investigator's Brochure.

Briefly, intravenous (IV) infusion of angiotensin II produces a sustained increase in MAP in normotensive animals, including rats, dogs, and rabbits (Campbell 2013). In animal models of hypotension, there are two key studies:

- In a sepsis model in pigs, treated with either NE or angiotensin II for 48 hours after a 12-hour period of untreated sepsis, angiotensin II was as effective as NE in restoring arterial BP and increased cardiac output (Corrêa 2014).
- In a septicemia model in sheep, infusion of angiotensin II was effective in restoring arterial BP and increased urinary output and creatinine clearance, despite a marked decrease in renal blood flow. In this model, angiotensin II improved renal function without major adverse effects on blood flows to other vital organs, blood lactate, or other biochemical variables (Wan 2009).

Furthermore, the range of angiotensin II administered in these animal models of septic shock was similar to the range of angiotensin II that has been used in humans with hypotensive shock (Chawla 2014; Whiteley 1996).

Pharmacokinetic studies in rats indicate that angiotensin II equilibrates rapidly and has a half-life in blood of less than 60 seconds (Al-Merani 1978).

No studies have been conducted to assess the genotoxicity of LJPC-501 because it is a naturally occurring peptide. There have been no classical reproductive or developmental studies conducted with exogenously administered angiotensin II.

4.5. Clinical Experience with Angiotensin II

GIAPREZA[™] (angiotensin II) injection for IV infusion (LJPC-501) is approved for use in the United States as a vasoconstrictor to increase blood pressure in adults with septic or other distributive shock.

In numerous clinical studies, angiotensin II has demonstrated significant effects on systemic and renal blood flow. Intravenous angiotensin II has been safely studied in patients with hypertension, aortic regurgitation, coronary artery disease, recent myocardial infarction, congestive heart failure, traumatic brain injury, chronic obstructive pulmonary disease, peripheral vascular disease, diabetes mellitus, congenital adrenal hyperplasia, primary hyperaldosteronism, renovascular hypertension, cirrhosis, and adrenal masses (Fraser 1980, Goldsmith 1993, Thomas 1991, Yunge 2000). Case reports support the use of angiotensin II to treat hypotension in patients suffering from vasopressor-resistant shock (Thomas 1991, Yunge 2000, Wray 1995). In addition, angiotensin II has been reported to successfully restore MAP in patients who have taken overdoses of angiotensin converting-enzyme (ACE) inhibitors and were refractory to catecholamines (Newby 1995, Trilli 1994).

In humans, infusion of 1.5-3.0 ng/kg/min angiotensin II was found to increase MAP (Campbell 2013, Nassif 1963). When synthetic angiotensin II was administered to 14 patients in hypotensive states, the drug was found to increase MAP to some degree in all patients, including those who were relatively unresponsive to other vasopressor agents (Nassif 1963). Data from a study by Chawla et al (Chawla 2014) support the safety and efficacy of angiotensin II in the treatment of patients who remain hypotensive despite receiving fluid therapy and vasopressor therapy. In that study, patients were randomized to receive angiotensin II acetate infusion or a placebo infusion plus the standard of care (SOC) treatment for severe hypotension. The titration protocol was designed to elucidate the dose of angiotensin II that was required (in conjunction with a NE dose of between 5-10 μ g/min) to achieve a MAP goal of 65 mmHg. The dose rate of angiotensin II administered was between 5 and 40 ng/kg/min. Norepinephrine doses were significantly lower for the angiotensin II cohort than for the placebo cohort, and the effect reached statistical significance at Hour 2. Upon cessation of the angiotensin II infusion, the need for NE was reestablished.

La Jolla completed a double-blind, placebo-controlled Phase 3 clinical study (ATHOS-3) of LJPC-501 in patients \geq 18 years old who remain hypotensive despite receiving fluid therapy and vasopressor therapy. Patients were randomized to receive LJPC-501 or a placebo infusion plus SOC treatment. A starting dose rate of 20 ng/kg/min was administered IV, and during the first 3 hours of administration could be titrated up to 200 ng/kg/min in order to achieve and maintain a MAP of 75 mmHg or higher. Results demonstrated a statistically significant improvement in MAP in LJPC-501-treated patients compared to placebo-treated patients. The percentage of patients obtaining a pre-specified target MAP was 70% with LJPC-501 compared to 23% with placebo (chi-square test p < 0.00001). In addition, LJPC-501 was generally safe and well tolerated in this population: 92% of placebo-treated patients compared to 87% of LJPC-501-treated patients experienced at least one AE, and 22% of placebo-treated patients compared to

14% of LJPC-501-treated patients discontinued treatment due to an AE. Although the study was not powered for a mortality endpoint, LJPC-501 showed a positive trend at Day 7 with 35% mortality in the placebo arm compared to 29% in the LJPC-501 arm (hazard ratio = 0.78; 95% CI: 0.53-1.16; p = 0.218, unstratified log-rank test) and at Day 28 with 54% mortality in the placebo arm compared to 46% in the LJPC-501 arm (hazard ratio = 0.78; 95% CI: 0.57-1.07; p = 0.123, unstratified log-rank test).

In a search of the literature, a single article was found on the use of angiotensin II in pediatric shock (Yunge 2000). The article reports on two children with severe septic shock. One had meningococcal septicemia and the other *Escherichia coli* septicemia. Both remained hypotensive despite high concentrations of conventional inotropes and vasopressors. The first child was given an infusion of angiotensin II that started at 100 ng/kg/min and increased to a maximum of 320 ng/kg/min over 24 hours. The second child was given an infusion of angiotensin II at 400 ng/kg/min and increased to a maximum of 800 ng/kg/min over 7 days. In both cases, there was significant improvement in clinical status, resulting in a rapid reduction in the concentration of inotropes required. Both patients successfully survived their septic episodes.

4.6. Summary of Known Risks

Forms of angiotensin II have been administered to patients and healthy subjects in multiple clinical studies since 1941. A systematic review of the literature identified more than 31,000 human subjects who were exposed to synthetic angiotensin II by IV infusion (Busse 2017). The most common symptoms reported in two or more studies were headache (including severe), sensation of chest pressure/tightness, dyspepsia/nausea, bradycardia, and orthostatic hypotension/dizziness.

In the Phase 3 study of LJPC-501 in critically ill adult patients(ATHOS-3), there was a higher incidence of venous and arterial thromboembolic events in patients who received GIAPREZA compared to placebo-treated patients (12.9% versus 5.1%). The major imbalance was in venous thromboses. Because of the risk of venous or arterial thrombotic or thromboembolic events, concurrent venous thromboembolism (VTE) prophylaxis is advised for adults treated with LJPC-501 (GIAPREZA[™] [angiotensin II] Prescribing Information). The risk of thrombosis in children treated with LJPC-501 is unknown, and it is recommended to follow your institution's guidelines for VTE prophylaxis in pediatric patients.

Other adverse events occurring with an incidence of at least 4% among adult patients treated with GIAPREZA and with a rate of at least 1.5% higher with GIAPREZA than with placebo are listed in Table 3. Risk of these or other adverse events in pediatric patients is unknown.

Adverse Event	GIAPREZA (LJPC-501) N=163	Placebo N=158
Thromboembolic events ^a	21 (12.9%)	8 (5.1%)
Deep vein thrombosis	7 (4.3%)	0 (0.0%)
Thrombocytopenia	16 (9.8%)	11 (7.0%)
Tachycardia	14 (8.6%)	9 (5.7%)
Fungal infection	10 (6.1%)	2 (1.3%)
Delirium	9 (5.5%)	1 (0.6%)
Acidosis	9 (5.5%)	1 (0.6%)
Hyperglycemia	7 (4.3%)	4 (2.5%)
Peripheral ischemia	7 (4.3%)	4 (2.5%)

Table 3:Adverse Reactions Occurring in $\geq 4\%$ of Patients Treated with GIAPREZA
and $\geq 1.5\%$ More Often than in Placebo-treated Patients in ATHOS-3

Source: GIAPREZA Prescribing Information

^a Including arterial and venous thrombotic events

Consistent with the mechanism of action and short half-life of angiotensin II, transient hypertension and hypotension are known risks of LJPC-501 treatment that may be mitigated by frequent or continuous monitoring of hemodynamic variables and appropriate dose titration.

A summary of the AEs observed in the Phase 3 study and risks of LJPC-501 treatment are provided in the Investigator's Brochure.

5. TRIAL OBJECTIVES AND ENDPOINTS

5.1. Primary Objective

• To evaluate the effect of LJPC-501 infusion on MAP or reduction in sum NE equivalent dosing, at Hour 2 after the start of LJPC-501, in pediatric patients who remain hypotensive despite receiving fluid therapy and vasopressor therapy

5.2. Primary Endpoint

- Proportion of patients with
 - a 25% increase in MAP over baseline (without an increase in sum NE equivalent dose [NED] from baseline) at 2 hours after the initiation of LJPC-501
 OR
 - a 25% reduction in NED from baseline (without a decrease in MAP from baseline) at 2 hours after the initiation of LJPC-501

5.3. Secondary Objectives

- To establish the safety and tolerability of LJPC-501 in pediatric patients
- To evaluate the change in MAP over 24 hours after the start of LJPC-501
- To evaluate the change in serum lactate concentrations
- To evaluate change in Pediatric Logistic Organ Dysfunction (PELOD) scores

5.4. Secondary Endpoints

- Adverse events, blood pressure (BP), heart rate (HR), and routine clinical safety laboratory testing including blood chemistry, hematology, and urine output
- Change in MAP from baseline to 24 hours
- Change in concentration of serum lactate from baseline to 2 hours and to 24 hours
- Change in PELOD score from Screening to 24 hours

5.5. Exploratory Endpoints

- Change in tissue oxygenation from baseline to 2 hours and to 24 hours
- Change in HR from baseline to 2 hours
- Change in sum NED from baseline to 24 hours
- 28-day all-cause mortality
- Number of ventilator days
- Number of days on a vasopressor
- Change in PRISM and PIM2 scores from Screening to 24 hours

La Jolla Pharmaceutical Company - Confidential 19 March 2018 (Version 2.0)

6. INVESTIGATIONAL PLAN

6.1. Study Rationale

Severe hypotension is associated with significant mortality, and the use of high doses of catecholamines in patients with severe hypotension is associated with poor outcomes. Given that LJPC-501 has recently been demonstrated to be efficacious and well-tolerated in adults with hypotension who do not respond to fluids and vasopressor therapy (Section 4.5), it is reasonable to hypothesize that LJPC-501 may also be efficacious and well-tolerated in pediatric patients with the same diagnosis.

This is an open-label, multi-center study. Pediatric patients, age 2 to 17 years, who remain hypotensive despite receiving fluid therapy and vasopressor therapy and are hospitalized in an ICU setting may be eligible to participate. Because severe hypotension is life threatening, and because the treatment options are limited for pediatric patients who remain hypotensive despite fluids and vasopressors, this study will examine a single LJPC-501 treatment arm, without a placebo-controlled arm. Efficacy of LJPC-501 will be measured by each patient's response over time. To assess multiple possible improved outcomes, the primary endpoint is a composite of the proportion of patients with an increase of 25% over Baseline MAP at Hour 2 after the initiation of LJPC-501, or with a 25% reduction in sum NED at Hour 2 after the initiation of LJPC-501.

Secondary endpoints will include the change in MAP at Hour 24, and the change in serum lactate concentrations. The risk of mortality will be assessed using the PELOD score at Hour 24. Safety and tolerability will be assessed throughout the study.

Exploratory endpoints will include tissue oxygen levels, HR, reduction in sum NED at Hour 24, all-cause mortality at 28 days, the number of days that patients spend on mechanical ventilation, and the number of days on vasopressors. Exploratory measures of the risk of mortality will include PRISM and PIM2 scores at Hour 24.

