6.2. Overall Study Design

The overall sequence of study events is shown in Figure 1. During Screening, patients will have their SOC vasopressors titrated to an age-, size-, and disease-appropriate MAP (Appendix A, Dellinger 2013) at the discretion of the Investigator. A minimum titration period of 2 hours, and a maximum of 48 hours, is required. The Screening MAP is calculated as the average of at least two once-hourly MAP readings during SOC vasopressor titration, and within 24 hours prior to LJPC-501 treatment initiation.

In the 15 minutes prior to initiation of LJPC-501 dosing, a baseline MAP will be documented. The Baseline MAP is the average of 3 recorded MAP values documented within 15 minutes prior to initiation of LJPC-501 (ie, at approximately -15 minutes, -5 minutes, and 0 minutes or just prior to initiation of LJPC-501 administration).

After obtaining informed consent from the patients' parent(s) or legal guardian(s), assent from the patients (per institutional requirements, as age appropriate, if possible), and confirmation of eligibility, patients will begin LJPC-501 treatment at a dose rate of 5 ng/kg/min. The goal at Hour 2 of LJPC-501 administration is to increase the Baseline MAP by 25% or to decrease the

sum NED by 25%. The LJPC-501 dose will be titrated during this period according to the guidelines in Section 8.3, to achieve a MAP above baseline, but less than 90 mmHg. Throughout treatment, the LJPC-501 dose rate may be increased to a maximum rate of 40 ng/kg/min, and decreased to a minimum of 1.25 ng/kg/min. If MAP exceeds 90 mmHg, SOC vasopressors should be down-titrated first, then LJPC-501 should be down-titrated if MAP remains \geq 90 mmHg. Any decision to increase the dose rate above 40 ng/kg/min must be made in consultation with Sponsor. With Sponsor approval, the dose rate may be increased to a maximum of 80 ng/kg/min. Unless adjustment is required for safety reasons, SOC vasopressor dosing should be decreased, but not increased, during the first 2 hours of LJPC-501 treatment (ie, up to the Hour 2 time point). MAP should not be allowed to decrease below baseline.

[figure not shown]

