8.2. Concomitant Medications and Procedures

All patients should be given maximal supportive therapy during the course of the study. All medications and supportive therapies (including renal replacement therapy and ventilation support) that are administered from Screening through the Day 28 follow-up, including the dose and indication, must be recorded on the appropriate CRF and in the source documents. Supportive therapy that is ongoing at baseline will be permitted during the treatment phase of the study. No other experimental therapy is permitted. Concomitant medications for other medical conditions are permitted as clinically indicated. Concomitant procedures, such as dialysis, mechanical ventilation, and relevant procedures used to diagnose or treat a serious adverse event (SAE), will also be recorded from screening through Day 28.

Start and stop date(s)/time(s), dose, and amount administered will be recorded for vasopressors administered up to 48 hours prior to, during, and after LJPC-501 administration. Total daily dose for each vasopressor administered through Day 28 may be recorded after completion of LJPC-501 administration.

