10.4. PELOD/PRISM/PIM2 Scoring

Risk scoring indices will include the PELOD, PRISM, and PIM2 scores (Table 6).

All components of the PELOD, PRISM, and PIM2 scores will be collected during Screening, employing data obtained no more than 6 hours prior to initiation of LJPC-501 dosing. In addition, all components of PELOD, PRISM, and PIM2 scores will be collected at Hour 24 after the initiation of LJPC-501. The PELOD score is the sum of the 6 individual item scores (Appendix C). The PRISM score is the sum of the 14 individual item scores (Appendix D). The PIM2 score is the sum of the 10 individual item scores (Appendix E).

PELOD	PRISM	PIM2	
	Common to All		
Systolic BP	Systolic BP	Systolic BP	
Pupillary reactions	Pupillary reactions	Pupillary reactions	
PaO ₂ /FiO ₂	PaO ₂ /FiO ₂	$FiO_2 \times 100/PaO_2$	
	Common to 2 Scores		
Heart rate	Heart rate		
PTT or INR	PT/PTT		
Glasgow score	Glasgow score		
PaCO ₂	PaCO ₂		
Mechanical ventilation		Mechanical ventilation during first hour in ICU	
	Unique		
AST/SGOT	Bicarbonate (mEq/L)	Base excess (mmol/L) in arterial or capillary blood	
Creatinine	Total bilirubin	High risk diagnosis score	
Platelets	Calcium	Low risk diagnosis score	
WBC	Potassium	Elective admission	
	Glucose	Recovery post procedure	
	Diastolic BP	Cardiac bypass	
	Respiratory rate		

Table 6: Assessments Included in Each Pediatric Mortality Risk Score

Abbreviations: AST=aspartate transaminase; BP=blood pressure; FiO₂=fractional inspired oxygen; ICU=intensive care unit; INR=international normalized ratio; mEq=milliequivalent; PaO₂=arterial oxygen partial pressure; PaCO₂=carbon dioxide partial pressure; PELOD=Pediatric Logistic Organ Dysfunction; PIM2=Pediatric Index of Mortality 2; PRISM=Pediatric Risk of Mortality; PT=prothrombin time; PTT=partial thromboplastin time; SGOT= serum glutamic-oxaloacetic transaminase; WBC=white blood cells.

Assessments for PELOD, PRISM, and PIM2 scores are drawn from multiple sources, and Investigators should ensure all assessments are performed within the time windows for Screening (within 6 hours prior to LJPC-501 administration) and Hour 24 (± 1 hour).

- Vital signs: systolic BP, diastolic BP, HR, RR
- Hematology and serum chemistry: PTT, INR, AST, creatinine, platelets, WBC, total bilirubin, calcium, potassium, glucose
- ABG: PaO₂/FiO₂, PaCO₂, bicarbonate, base excess

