APPENDIX C. PELOD SCORING

	Points assigned			
Organ system and variable	0	1	10	20
Neurologic*				
Glasgow coma score	12–15 and	7–11	4–6 or	3
Pupillary reaction	Both reactive		Both fixed	
Cardiovascular				
Heart rate, beats/min				
< 12 years	≤ 195		> 195	
\geq 12 years	≤ 150		> 150	
	and		or	
Systolic blood pressure, mm Hg				
< 1 mo	> 65		35–65	< 35
≥ 1 mo-< 1 yr	> 75		35–75	< 35 < 45
\geq 1 yr-< 12 yr	> 85 > 95		45-85	< 45 < 55
≥ 12 yr	2 95		55–95	< 22
Renal				
Creatinine, μmol/L (mg/dL)				
< 7 d	< 140 (< 1.59)		≥ 140 (≥ 1.59)	
≥ 7 d–< 1 yr	< 55 (< 0.62)		≥ 55 (≥ 0.62)	
≥ 1 yr–< 12 yr	< 100 (< 1.13)		≥ 100 (≥ 1.13)	
≥ 12 yr	< 140 (< 1.59)		≥ 140 (≥ 1.59)	
Respiratory				
PaO ₂ :FiO ₂ ratio, mm Hg	> 70		≤ 70	
	and		or	
PaCO₂, mm Hg (kPa)	≤ 90 (≤ 11.7)		> 90 (> 11.7)	
	and			
Mechanical ventilation [†]	No ventilation	Ventilation		
Hematologic				
Leukocyte count, × 10º/L	≥ 4.5	1.5-4.4	< 1.5	
	and	or		
Platelet count, $ imes$ 10 $^{\circ}$ /L	≥ 35	< 35		
Hepatic				
Glutamic oxaloacetic transaminase, IU/L		≥ 950		
Prothrombin time, % of standard (international normalized ratio)	and > 60 (< 1.40)	or ≤ 60 (≥ 1.40)		

Source: Leteurtre 2003

Abbreviations: PaO₂ arterial oxygen partial pressure; FiO₂=fractional inspired oxygen; PaCO₂=carbon dioxide partial pressure.

Note: For the Glasgow coma score, use the most recent, non-sedated value. For pupillary reactions, nonreactive pupils must be > 3 mm; do not assess after iatrogenic pupillary dilation. The use of mask ventilation is not considered to be mechanical ventilation.

Parameter	Infants	Children	All ages	Score
Systolic Blood Pressure (mmHg)	130-160	150-200		2
	55-65	65-75		2
	> 160	> 200		6
	40-54	50-64		6
	< 40	< 50		7
Diastolic Blood Pressure (mmHg)			> 110	6
Heart Rate (beats/min)	> 160	> 150		4
	< 90	< 80		4
Respiratory Rate (breaths/min)	61-90	51-70		1
	> 90	> 70		5
	apnea	apnea		5
PaO ₂ / FiO ₂ (mmHg) ^a			200-300	2
· · · · · ·			< 200	3
PaCO ₂ (mmHg)			51-65	
· · · · ·			> 65	
Glasgow Coma Score ^b			< 8	6
Pupillary Reactions			unequal or dilated	4
			fixed and dilated	10
PT/PTT			$1.5 \times \text{control}$	2
Total Bilirubin			> 3.5	6
Potassium (mEq/L)			3.0-3.5	1
			6.5-7.5	1
			< 3.0	5
			> 7.5	5
Calcium			7.0-8.0	2
			12.0-15.0	2
			< 7.0	6
			> 15.0	6
Glucose			40-60	4
			250-400	4
			< 40	8
			> 400	8
HCO ₃ (mEq/L) ^c			< 16	3
			> 32	3

Source: Pollack 1988

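### Total PELOD at Hour 24 is used to assess mortality risk, yet one item scores the blood pressure that the drug is titrated to raise, so 10 of 71 points can go with no change in any other organ item

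*Protocol*

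**What the plan says.** Section 6.1 gives PELOD its role: "The risk of mortality will be assessed using the PELOD score at Hour 24". The matching secondary endpoint in section 5.4 is "Change in PELOD score from Screening to 24 hours". Section 10.4 forms the score as a plain sum of six items and lists its components in a table titled "Assessments Included in Each Pediatric Mortality Risk Score".

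In Appendix C the cardiovascular item has two inputs, heart rate and "Systolic blood pressure, mm Hg". Vasopressor dose does not enter. At 1 to <12 years, SBP above 85 mmHg scores 0, 45-85 scores 10 and below 45 scores 20. At ≥12 years the bands are above 95, 55-95 and below 55. Heart rate above 195 (<12 years) or 150 (≥12 years) scores 10 by itself.

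On the drug, section 4.3 says that "angiotensin II induces peripheral vasoconstriction", and section 6.2 sets the early aim: "The goal at Hour 2 of LJPC-501 administration is to increase the Baseline MAP by 25% or to decrease the" sum norepinephrine-equivalent dose by the same percentage. Section 6.6 asks that MAP stay above baseline and below 90 mmHg during titration. Section 8.5.5 requires all Hour 24 procedures to be finished before down-titration begins in patients who are stopping. Section 6.1 confirms a single arm without placebo.

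**The concern.** A scored component of the mortality-risk measure is closely tied to the quantity being titrated. MAP is already covered by the primary endpoint at Hour 2 and by the secondary MAP endpoint at Hour 24. To that extent a fall in total PELOD repeats those results. A reader of 6.1 together with 5.4 could take the fall as lower mortality risk when no other organ item has moved. Without a control arm, nothing in the data shows how much of a fall comes from the pressure item alone. With 10 to 30 patients, a few 10-point steps are visible in a mean change.

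**Working it through.** The protocol states no derived figure on this point, so there is nothing to reproduce. The check scores Appendix C before and after a rise in pressure.

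**Inputs.** Item maxima, SBP bands and heart-rate limits come from Appendix C. Lower MAP limits by age come from Appendix A: 50, 60 and 65 mmHg. Pulse pressure (PP) is not in the protocol and is an assumption, ranged over 20-50 mmHg.

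**1. Scale.** Neurologic 20 + cardiovascular 20 + renal 10 + respiratory 10 + hematologic 10 + hepatic 1 = 71. Without the cardiovascular item: 71 − 20 = 51. One 10-point step is 10/71 = 14% of the scale.

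**2. The step.** With heart rate within its limit and all other items fixed, SBP 85 to 86 mmHg (1 to <12 years) moves the item from 10 to 0, as does 95 to 96 (≥12 years). With heart rate above its limit the item stays at 10.

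**3. An illustrative child of 6 years.** MAP = (SBP + 2 × DBP)/3.
- 82/52: (82 + 104)/3 = 62.0 mmHg, item score 10.
- 88/56: (88 + 112)/3 = 66.7 mmHg, item score 0.
- The MAP rise is 66.7/62.0 − 1 = 7.5%, under a third of the 25% primary criterion. Both MAP values lie in the Appendix A range for that age (60-90). Total PELOD falls by 10; without the cardiovascular item the change is 0.

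**4. MAP rise needed to reach the cut-off from the Appendix A lower limit.** SBP = MAP + (2/3) × PP. The rise is (cut-off − SBP)/MAP if PP stays fixed, or cut-off/SBP − 1 if PP scales with MAP.

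| Age, starting MAP | PP | SBP | Item score | Rise, PP fixed | Rise, PP scaled |
|---|---|---|---|---|---|
| 2-4 y, 50 | 20 | 63.3 | 10 | 43% | 34% |
| | 30 | 70.0 | 10 | 30% | 21% |
| | 40 | 76.7 | 10 | 17% | 11% |
| | 50 | 83.3 | 10 | 3% | 2% |
| 5-9 y, 60 | 20 | 73.3 | 10 | 19% | 16% |
| | 30 | 80.0 | 10 | 8% | 6% |
| | 40 | 86.7 | 0 | none to lose | none to lose |
| | 50 | 93.3 | 0 | none to lose | none to lose |
| ≥12 y, 65 | 20 | 78.3 | 10 | 26% | 21% |
| | 30 | 85.0 | 10 | 15% | 12% |
| | 40 | 91.7 | 10 | 5% | 4% |
| | 50 | 98.3 | 0 | none to lose | none to lose |

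Of the nine rows that start at 10 points, a 25% MAP rise crosses the cut-off under both assumptions in six, only with scaled PP in two, and under neither in one. From higher starting MAPs more patients already score 0. For example, at age 7 and MAP 70 mmHg, PP 20 gives SBP 83.3 (10 points, rise needed about 2%), while PP 30 gives SBP 90.0 (0 points).

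**5. Effect on a mean.** If k of n patients lose 10 points in this way, the mean change moves by 10k/n. As an illustration only, 3 of 15 gives 2 points. The protocol gives no basis for k.

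**The case against.** The other side has several sound points.

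- The protocol never calls PELOD independent of blood pressure. The secondary objective is only to evaluate its change, and the table in 10.4 openly lists systolic pressure as common to all three scores. This stands. A reader might infer from 6.1 that total PELOD is offered as evidence beyond the pressure effect, but the text does not say so. What remains is that 6.1 attaches mortality risk to the total without any caution about the overlap.
- Appendix C reproduces a sourced score, and using it as built is not an error. Nothing in the documents supports a version without the cardiovascular item as a replacement. This also stands: hypotension is part of the condition studied, so the total should stay as the endpoint.
- Screening pressure is itself supported by vasopressors, and sections 6.2 and 8.3.1 aim to reduce them during treatment. That can offset the rise and is one reason why the bias cannot be sized.
- Component summaries often belong in the SAP, which section 12 announces and which was not available here. The role given to PELOD in 6.1 is protocol text, however, and can be limited there.
- The consequence is limited. Success rests on the primary composite, reporting is descriptive, 28-day all-cause mortality is recorded, and section 10.4 assigns the worst score when Hour 24 values are missing through death or treatment failure.

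**Conclusion.** The point holds in a limited form. For a patient still on drug at Hour 24, with Screening SBP in the 10-point band and heart rate within its limit, a small pressor rise can remove 10 of 71 points (14%) with no change in any other organ item. Patients already above 85 or 95 mmHg at Screening have no SBP points to lose. How many patients fall in each group is not stated, so neither the frequency nor the net size of the bias can be given. The pulse pressures and the worked child are assumptions.

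Two stronger readings are not supported. A reader might count the full 20 points of the cardiovascular item as at stake. SBP cannot be below MAP, and the Appendix A lower limits (50, 60 and 65 mmHg) lie above the 20-point thresholds for those ages (45 mmHg under 12 years, 55 mmHg from 12 years). A patient within those ranges therefore cannot score 20 on SBP. A reader might also infer that renal replacement started after Screening would be scored as renal recovery, because Appendix C scores creatinine alone. Section 8.2 only requires such therapy to be recorded. Nothing in the documents shows how often it would start, or that it would bring creatinine below the cut-off by Hour 24.

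**What to change.** - **Sections 5.4 and 10.4:** keep change in total PELOD as the endpoint. Prespecify beside it a descriptive summary of the change with the cardiovascular item removed (neurologic, renal, respiratory, hematologic and hepatic items; range 0-51).
- **Section 6.1:** say that total PELOD includes a blood-pressure item that the drug directly affects, and that a fall in the total is not read as lower mortality risk unless it is also seen without that item. Say also that mortality is described by the 28-day all-cause deaths already listed in section 5.5.

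The renal item needs no re-scoring. The cost is a wording change and one extra summary from components already collected; no visit, assessment or treatment rule changes. The downside is that the reported PELOD improvement may be smaller.
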